Study Protocol

Official title	An Open-Label, Two-Arm, Phase II Clinical Trial of Neoadjuvant mFOLFOX6 Combined with Citrus Flavonoid Tablets (Alvenor) for Locally Advanced Rectal Cancer with High YWHAB Expression
No.Version	2.1
Document date	2025-04-23
NCT number	Not available at present

**The Sixth Affiliated Hospital of Sun Yat-sen
University**

1. Background

(1) Research status at home and abroad

Colorectal cancer (CRC) is the third most common malignant tumor globally, with over 1.8 million new cases annually, accounting for about 10% of all new malignant tumors, and causing more than 910,000 deaths [1]. In recent years, the incidence and mortality of CRC in China have been on the rise. By 2020, CRC had become the second most common malignant tumor in China, with 550,000 new cases annually and a mortality rate ranking fifth, with 280,000 new deaths in 2020 [2]. The disease burden of CRC in China is continuously increasing, and the prevention and control efforts for CRC remain a significant challenge. The rectum ends at the upper edge of the functional anal canal, defined as the palpable upper edge of the puborectalis muscle of the anal sphincter and the anorectal ring. Rectal cancer refers to cancerous lesions that occur in the rectum, located below the virtual line from the sacral promontory to the upper edge of the symphysis, as determined by MRI. Determining the optimal treatment plan for rectal cancer patients is a complex process. Besides deciding whether the surgery is curative or palliative, it is also necessary to consider potential functional outcomes after treatment, including maintaining or restoring normal bowel function, anal control, and preserving urinary and reproductive functions. For patients with low-lying rectal cancer, achieving tumor cure while minimizing the impact on quality of life is particularly challenging [3]. Moreover, compared to colon cancer, rectal cancer patients have a higher risk of pelvic recurrence, and local recurrence of rectal cancer is associated with a poorer prognosis [4-6].

Currently, the multimodal treatment for stage II or III rectal cancer typically includes preoperative chemoradiotherapy with fluorouracil-based regimens, total mesorectal excision (TME), and postoperative adjuvant chemotherapy[7-8]. The FOWARC study conducted by our center has demonstrated that, compared to standard preoperative chemoradiotherapy, patients who received mFOLFOX6 neoadjuvant chemotherapy showed no significant differences in tumor downstaging, disease-free survival (DFS), local recurrence rate, or overall

survival. However, the incidence of postoperative anastomotic leakage was significantly lower in patients receiving only mFOLFOX6 neoadjuvant chemotherapy, with better anal function and improved long-term quality of life. This suggests that mFOLFOX6 neoadjuvant chemotherapy can partially replace preoperative chemoradiotherapy, effectively avoiding radiotherapy-related side effects without compromising treatment efficacy. The findings have been cited in the NCCN international guidelines[9-11]. Studies have shown that tumor downstaging (ypTNM 0-I stage) is significantly associated with better DFS in locally advanced rectal cancer patients who receive neoadjuvant therapy[9-11]. The FOWARC study found that about 35% of locally advanced rectal cancer patients who received mFOLFOX6 neoadjuvant chemotherapy had tumor downstaging. This indicates that some patients may be less sensitive to mFOLFOX6 neoadjuvant chemotherapy. Identifying and screening out these patients who are resistant to mFOLFOX6 treatment, and further improving their tumor downstaging rate and prognosis through mFOLFOX6 chemotherapy combined with targeted therapy, holds promise.

The dysregulation of the Wnt/β-catenin signaling pathway is closely linked to the development and progression of various cancers, particularly in colorectal cancer (CRC) [12]. The YWHA (14-3-3) family of proteins is widely expressed in eukaryotic cells, including seven subtypes: 14-3-3 β (YWHAB), 14-3-3 γ (YWHAG), 14-3-3 ϵ (YWAH), 14-3-3 ζ (YWAZ), 14-3-3 σ (YWHAS) and 14-3-3 τ/θ (YWAQ)[13].. These 14-3-3 isoforms exhibit highly conserved structures across different species and can form both homodimers and heterodimers, acting as molecular connectors through protein-protein interactions [14]. As the central hub of various signaling pathways, 14-3-3 proteins are involved in numerous cellular processes, including cell cycle regulation, protein transport, apoptosis, and neuronal plasticity [13-15]. More importantly, dysregulation of 14-3-3 proteins is associated with multiple diseases, such as cancer, autoimmune disorders, and metabolic disorders [13,16]. Our preliminary research has identified that the amplification of YWHAB (14-3-3 β) is a key

driver of copy number variations (CNVs) in cancer cells and is associated with poor outcomes in CRC patients, suggesting its potential as a biomarker for prognosis. Furthermore, experimental evidence from cell studies and mouse models indicates that YWHAB enhances glycolysis and nucleotide metabolism, thereby promoting chemotherapy resistance in colorectal cancer (CRC). Mechanistically, YWHAB interacts with β -TrCP and competitively binds to β -catenin, inhibiting the degradation of β -catenin mediated by β -TrCP, thus promoting the development and progression of CRC and its chemotherapy resistance. Additionally, through large-scale molecular docking and drug binding affinity screening, we discovered that FDA-approved drugs hesperidin and diosmin can specifically block the interaction between YWHAB and β -TrCP, significantly enhancing the sensitivity of YWHAB high-expressing CRC organoids and patient-derived xenografts (PDX) to FOLFOX treatment. Therefore, our research has provided a deeper understanding of the chemotherapy resistance mechanism in YWHAB high-expressing CRC. The expression level of YWHAB can serve as a potential biomarker for predicting chemotherapy sensitivity in CRC patients and for achieving precise chemotherapy. Blocking the YWHAB/ β -TrCP/ β -catenin signaling axis is expected to be an important approach to improve the chemotherapy sensitivity of YWHAB high-expressing CRC patients.

Flavonoids are a major class of polyphenolic compounds naturally found in plants[17]. Previous studies have reported that flavonoids have multiple therapeutic effects, such as anti-inflammatory, antioxidant, and anti-cholesterol activity[18]. Naringin and dasiglucoside are common flavonoids found in citrus fruits, with highly similar molecular structures, known for their antioxidant properties, which help protect cells from damage by free radicals. Research has shown that naringin and dasiglucoside can support heart health by enhancing vascular function and reducing inflammation[18-19], and they have been proven beneficial to the brain, liver, and eyes. It has been reported that naringin and dasiglucoside have anti-inflammatory, antioxidant, anti-tumor, and antibacterial

therapeutic potential[20-22]. Clinical trials and practices have confirmed the therapeutic effects of naringin and dasiglucoside on various diseases, including cardiovascular disease, neurological disorders, type 2 diabetes, venous ulcers, hemorrhoids, fatty liver disease associated with metabolic dysfunction, and cancer[23]. Previous studies [23] have found that naringin can inhibit the protein expression level of nitric oxide synthase (iNOS), thereby reducing the production of nitrogen dioxide and prostaglandin E2 (PGE2); therefore, naringin is considered an inhibitor of cyclooxygenase-2 and iNOS, which may explain its anti-tumor and anti-inflammatory properties. A study in 2022 found that naringin has chemopreventive potential in colorectal cancer (CRC) induced by 1,2-dimethylhydrazine (DMH), and naringin prevents CRC in vivo by regulating the Smad4 and activin A signaling pathways[24]. Another study reported that hesperidin can effectively prevent the incidence of intestinal tumors in mice induced by azoxymethane [25]. In our preliminary research, we discovered through microscale thermophoresis (MST) experiments that hesperidin has a strong binding affinity with YWHAB protein. Both in vitro and in vivo experiments have shown that hesperidin and docetaxel can effectively inhibit the interaction between YWHAB and β -TrCP. Animal experiments further suggest that, compared to the FOLFOX regimen alone, combining citrus flavonoid tablets (Aimalang, each tablet containing 500mg of citrus flavonoids, 90% docetaxel, and 10% hesperidin) with the FOLFOX regimen can enhance the inhibitory effect of FOLFOX on PDX tumors. These in vitro and in vivo results fully confirm that the combination of FOLFOX and citrus flavonoid tablets (Aimalang) can serve as a potential treatment option for patients with high YWHAB expression CRC, although this needs to be further confirmed through prospective clinical trials.

Although the efficacy of citrus flavonoid tablets in treating various diseases has been confirmed through extensive clinical research and practice, most clinical trials use 300-600 mg of pure hesperidin for oral supplementation. However, due to its extremely low water solubility, hesperidin has a relatively low bioavailability [21,26,27]. After comprehensive consideration, we plan to use

citrus flavonoid tablets (Aimalang) as an alternative to citrus flavonoids in our clinical trials. In clinical practice, citrus flavonoid tablets (Aimalang) are commonly used to treat various symptoms associated with venous and lymphatic insufficiency, as well as acute hemorrhoids. Our preliminary studies have shown that docetaxel, hesperidin, and citrus flavonoid tablets (Aimalang) can effectively inhibit the interaction between YWHAB and β -TrCP, thereby enhancing the anti-tumor effects of FOLFOX. Furthermore, Aimalang has been clinically applied, and its safety has been confirmed. Therefore, based on our preliminary research and safety findings, using Aimalang as an alternative to hesperidin to explore the neoadjuvant treatment effects of FOLFOX combined with Aimalang in locally advanced rectal cancer with high YWHAB expression is both safe and reasonable.

A common strategy to improve tumor regression in patients with locally advanced rectal cancer is to enhance neoadjuvant therapy by adding systemic chemotherapy before radiotherapy and chemotherapy. Several Phase II clinical trials have shown that [28-31] systemic adjuvant chemotherapy before radiotherapy and chemotherapy can enhance the anti-tumor response in patients with large primary tumors near the mesorectal fascia. In these trials, the proportion of patients achieving pathological complete remission slightly improved after systemic adjuvant chemotherapy before radiotherapy and chemotherapy. In 2004, a German clinical trial named CAO/ARO/AIO-94 established preoperative infusion of fluorouracil as the standard combination therapy for locally advanced rectal cancer [32]. In 2015, the CAO/ARO/AIO-04 trial [33] added oxaliplatin to neoadjuvant radiotherapy and chemotherapy based on fluorouracil, significantly improving the disease-free survival rate in patients with cT3-4 or cN1-2 locally advanced rectal cancer. The protocol established by CAO/ARO/AIO-04 is also considered a new treatment option for patients with locally advanced rectal cancer. Our center has conducted a series of prospective studies in the field of adjuvant/neoadjuvant chemotherapy for locally advanced rectal cancer, such as the FOWARC study, and the relevant research findings have

been frequently cited in NCCN guidelines [9-11]. The mFOLFOX6 double-drug regimen (5-fluorouracil and leucovorin calcium in combination with oxaliplatin) is a highly potent chemotherapy regimen recommended by guidelines such as NCCN, EMSO, and CSCO for the first-line treatment of advanced colorectal cancer. However, it remains unclear whether the mFOLFOX6 double-drug regimen combined with Apatinib can enhance the treatment outcomes for patients with YWHAB high-expressing locally advanced rectal cancer. This requires further clinical research to confirm.

(2) Significance of the study

This study aims to conduct a prospective, open-label, double-arm, Phase II clinical trial. For patients with locally advanced rectal cancer, YWHAB immunohistochemical staining will be performed on colonoscopy biopsy specimens to identify patients with high YWHAB expression. These patients will then be randomly assigned to either the mFOLFOX6 treatment group or the mFOLFOX6 combined with Citrus Flavonoid Tablets (Aimalang) treatment group for neoadjuvant therapy. After completing 4-6 cycles of neoadjuvant chemotherapy, patients will undergo preoperative assessments by their attending physicians and have their tumors surgically removed by a specialized colorectal surgery team. Postoperatively, they will receive 6-8 cycles of adjuvant chemotherapy. The effectiveness and safety of the mFOLFOX6 combined with Citrus Flavonoid Tablets (Aimalang) regimen in neoadjuvant therapy for YWHAB high-expression locally advanced rectal cancer patients will be evaluated. This includes assessing the proportion of patients achieving tumor downstaging, the proportion of patients achieving pathological complete remission, the three-year disease-free survival rate, overall survival time, and tumor regression grade (TRG). The study is based on the team's previous basic research, animal experiments, and the clinical safety of Citrus Flavonoid Tablets (Aimalang), aiming to improve the efficacy of YWHAB high-expression locally advanced rectal cancer patients and benefit more patients.

2. Research design and purpose

2.1 Overall design of the study

This study is a prospective, open, double-arm, phase II clinical trial to explore the mFOLFOX6 combined with citrus flavonoid tablets (Aimalang) regimen as neoadjuvant therapy for YWHAB high expression locally advanced rectal cancer. The study design is in accordance with ethical requirements.

2.2 Research purpose

Main research objectives:

To evaluate the proportion of patients achieving tumor downstaging (ypTNM 0-I stage) in YWHAB high-expressing locally advanced rectal cancer treated with mFOLFOX6 combined with Citrus Flavonoid Tablets (Aimalang) as a neoadjuvant therapy, to provide evidence that Citrus Flavonoid Tablets (Aimalang) enhances the effectiveness of the mFOLFOX6 regimen in this patient population.

Secondary study objectives:

Efficacy evaluation: The proportion of pathological complete remission, 3-year disease-free survival (DFS), overall survival time (OS) and tumor regression grade TRG were evaluated in patients with YWHAB high expression locally advanced rectal cancer treated with mFOLFOX6 combined with citrus flavonoid tablets (Aimalang) as neoadjuvant therapy.

Safety evaluation: The treatment-related adverse reaction rate (grade 3 or above) of mFOLFOX6 combined with citrus flavonoid tablets (Aimalang) regimen for neoadjuvant treatment of YWHAB high expression local advanced rectal cancer patients was evaluated.

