2.3 Study endpoints

Main endpoints and definitions:

This study primarily evaluates the proportion of patients with YWHAB

high expression locally advanced rectal cancer who achieve tumor downstaging (ypTNM 0-I stage) after neoadjuvant therapy with mFOLFOX6 combined with Citrus Flavonoid Tablets (Aimianlang). The tumor downstaging rate (ypTNM 0-I stage) refers to the percentage of patients with locally advanced rectal cancer who, after receiving neoadjuvant chemotherapy with mFOLFOX6 or mFOLFOX6 + Citrus Flavonoid Tablets (Aimianlang), have their postoperative pathological stage of the surgical specimen classified as ypTNM 0-I stage.

Secondary endpoints and definitions:

- (1) The degree of pathological remission is defined as follows: ① Complete Remission (CR): All tumor target lesions have disappeared, no new lesions have appeared, and tumor markers are normal, lasting at least 4 weeks. ② Partial Response (PR): The sum of the maximum diameters of tumor target lesions has decreased by at least 30%, lasting at least 4 weeks. ③ Stable Disease (SD): The sum of the maximum diameters of tumor target lesions has not decreased by more than PR, or increased by less than PD. ④ Disease Progression (PD): The sum of the maximum diameters of tumor target lesions has increased by at least 20%, or new lesions have appeared.
- (2) The 3-year disease-free survival rate (DFS) is the proportion of patients who have not experienced any of the following events from the start of randomization to the end of year 3: disease progression, surgical gross/microscopic tumor residue, local recurrence, distant metastasis, or death for any reason, whichever occurs first.
- (3) Overall survival time (OS) is the time from randomization to death for any reason.
- (4) Tumor regression grading TRG: TRG 0 means no residual tumor cells, TRG 1 means a single cell or a small group of cells; TRG 2 means residual cancer with a proliferative response to connective tissue; TRG 3 means minimal evidence of tumor response.
- (5) Safety indicators, treatment-related adverse reaction rate (grade III and

above): Antitumor drugs/therapy In clinical trials, drug adverse reactions determined to be related to drug therapy at grade III and above, excluding nonspecific infusion reactions.

3. Selection and withdrawal of subjects

3.1 Inclusion criteria:

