4.1 Study treatment grouping

This study is a prospective, open-label, double-arm, Phase II clinical trial that includes a neoadjuvant treatment group using the mFOLFOX6 regimen and a neoadjuvant treatment group combining the mFOLFOX6 regimen with Citrus Flavonoid Tablets (Aimalang). The study aims to enroll patients with locally advanced rectal cancer who are in clinical stage I, II, or III. Endoscopic biopsy specimens will be collected for YWHAB immunohistochemical testing to identify patients with high YWHAB expression in locally advanced rectal cancer. These patients will then be randomly assigned to either the mFOLFOX6 treatment group or the mFOLFOX6 combined with Citrus Flavonoid Tablets (Aimalang) treatment group for neoadjuvant therapy. The mFOLFOX6 regimen involves 4-6 cycles before surgery and 6-8 cycles after surgery, with each cycle lasting 14 days: on day 1, 85 mg/m² of oxaliplatin is administered intravenously over 180 minutes; on day 1, 400 mg/m² of leucovorin is administered intravenously over 120 minutes; and on day 1, 2400 mg/m² of 5-fluorouracil is administered continuously intravenously for 46 hours. The Citrus Flavonoid Tablets (Aimalang) treatment regimen involves taking 500mg of Citrus Flavonoid Tablets (Aimalang) orally three times daily, with doses given on days 1-14 of each 14-day cycle.

This trial allows for dose adjustments. Patients who experience disease progression during neoadjuvant therapy may stop the study treatment and directly undergo surgery or follow local guidelines. If a patient cannot tolerate the planned 6 cycles of neoadjuvant therapy, early surgery can be considered. Any patient who has received another anticancer regimen before surgery will stop the study treatment and be managed according to local guidelines. The postoperative

treatment for both groups is determined by the investigator, which may include continuing the mFOLFOX6 regimen combined with Citrus Flavonoid Tablets (Aimalang). It is important to note that all patients in the control group are prohibited from taking Citrus Flavonoid Tablets (Aimalang) without authorization during the trial. If a patient needs to take this medication for any reason, they should consult their primary physician, who will decide whether to use an alternative or discontinue the patient's participation in the trial.

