7.5.2 Judgment of the relationship between adverse events and study treatment

The following criteria should be used to assess the relationship between adverse events and treatment:

- It is likely to be relevant (must have the first three): This category refers to adverse events for which there is a high degree of certainty that they are related to the investigational drug. An adverse event may be considered "likely to be relevant" if the following criteria are met:
 1. The occurrence of adverse events is associated with the use of drugs in a reasonable time.
 2. The known patient disease status, environmental or toxic factors or other treatments used by the patient do not reasonably explain the adverse event.
 3. After the dose is stopped or reduced, the adverse reactions will disappear or be alleviated. (However, there are some important exceptions, some drug-related adverse reactions will not disappear even after the drug is stopped; such as: (1) bone marrow suppression, (2) delayed motor dysfunction)
 4. The adverse events were consistent with the pattern of suspected drug reactions.
 5. When used again, the adverse event reappeared.
- May be related (must have the first two): This category refers to adverse events that are unlikely to be related to the administration of the investigational drug but cannot be definitively excluded from association. An adverse event may be considered "may be related" if the following criteria are met:

1. The occurrence of adverse events is associated with the use of drugs in a reasonable time.
2. Adverse reactions may be caused by the patient's disease status, environment or toxic factors or other concomitant treatments used by the patient.
3. The adverse events were consistent with the pattern of suspected drug reactions.

- May be irrelevant (must have the first two): This category applies to adverse events that meet the following criteria:
 1. The occurrence of adverse events is not reasonably time-related to drug use.
 2. Adverse events were clearly caused by the patient's disease status, environment or toxic factors or other concomitant treatments used by the patient.
 3. The adverse events did not conform to the pattern of suspected drug reactions.
 4. When the drug was used again, the adverse events did not occur or worsen.

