8.1 Analysis of population

- Informed Consent Set ICS: This analysis set will include all subjects who have signed an informed consent form.
- Intention-to-treat (ITT) analysis set: According to the principle of intention-to-treat analysis, all patients who were randomly assigned to the group at the time of randomization were analyzed according to the group into which they were assigned. This analysis set is the main analysis set for

efficacy endpoints.

- The Full Analysis Set (FAS) is defined as the group of all participants who were enrolled and received at least one dose of the study drug, following the intention to treat (ITT) principle. In analyses based on the FAS, participants are included according to their assigned group at enrollment, regardless of the actual treatment they received;
- In line with the protocol analysis set (Per-Protocol Set, PPS), ITT patients who did not experience significant protocol deviations that affected the efficacy assessment were included. The PP population was used for sensitivity analysis of the primary and key secondary efficacy endpoints.
- Safety set (Safety Set, SS): Will include all subjects who have received at least one study drug treatment. The safety set is the primary population for safety analysis.

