8.4 Safety analysis and statistical methods

The security analysis will be based on the security set. The security analysis is limited to descriptive statistical summaries, including but not limited to the following aspects, which will be described in the statistical analysis plan:

- Summary of adverse events (all-cause and treatment-related);
- Incidence and severity of adverse events (all-cause and treatment-related);
- Summary of details of serious adverse events;
- Analysis of adverse event correlation;
- Abnormal occurrence of laboratory indicators, vital signs and electrocardiogram data.

The security analysis will be based on descriptive statistical summaries and based on the security set.

This study will use the standard medical terminology set (MedDRA) of pharmaceutical management to code adverse events. The study will use tables to list all adverse events, drug-related adverse events, serious adverse events, and drug-related serious adverse events that occurred during treatment, according to the NCI CTCAE version 6.0 standard and using the worst grading. Additionally, the study will summarize the laboratory test parameters during the research period according to the NCI CTCAE version 6.0 standard and using the worst grading.

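### No between-arm safety estimate is specified, and the safety endpoint rests on drug-relatedness judged open-label, so it does not cleanly measure the severe toxicity the tablet adds

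*Combined protocol and SAP*

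**What the plan says.** - **Objective (2.2).** The safety evaluation concerns "The treatment-related adverse reaction rate (grade 3 or above) of mFOLFOX6 combined with citrus flavonoid tablets (Aimalang) regimen", in the neoadjuvant setting. No comparator is named.
- **Endpoint (2.3, item 5).** It counts "drug adverse reactions determined to be related to drug therapy at grade III and above, excluding nonspecific infusion reactions". It is not limited to one arm, and it does not say which relatedness categories of 7.5.2 count as related.
- **Relatedness (7.5.2).** There are four categories. The strongest covers events for which "there is a high degree of certainty that they are related to the investigational drug", and requires among other things that the patient's other treatments do not reasonably explain the event. The next category is described as unlikely to be related, though a link cannot be ruled out.
- **Analysis (8.4).** "The security analysis is limited to descriptive statistical summaries". The list is open-ended, covers all-cause as well as treatment-related events by severity, and leaves detail to a statistical analysis plan. It mentions neither arms, nor a difference, nor a confidence interval.
- **Population (8.1).** The Safety Set "Will include all subjects who have received at least one study drug treatment", so it includes control patients.
- **Design (4.1).** Open-label; patients are "randomly assigned to either the mFOLFOX6 treatment group or the mFOLFOX6 combined with Citrus Flavonoid Tablets (Aimalang) treatment group". Treatment after surgery is left to the investigator in both groups and may include the tablet.
- **Contrast with survival (8.3).** Disease-free and overall survival get a log-rank test and Cox hazard ratios between groups.

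**The concern.** Up to surgery both arms are planned to receive mFOLFOX6, and only one receives the tablet. The rate in the combination arm alone will largely reflect mFOLFOX6. The added harm of the tablet can be read only from a contrast with control, and the plan names no such contrast.

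Nor is the chosen endpoint a good basis for one. Whether an event counts depends on a causality judgement by someone who knows the arm and has one more drug to suspect in the tablet arm. If that judgement differs by arm, the attributed rates differ even when the events do not. The protocol's own rules give the assessor limited help. Improvement after stopping or reducing the dose is one criterion in 7.5.2, but for severe haematological or liver events 4.2.4 has all the drugs reduced together, so improvement cannot separate them.

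At stake is whether a claim of benefit comes with a matching estimate of harm and its uncertainty. Two bare percentages of attributed reactions could be read as showing no added toxicity, or as showing some, when neither is established.

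**Working it through.** **1. Is there a safety figure to reproduce?** No. The plan gives no expected severe-toxicity rate, precision or power for safety. The only usable input is the total of 236 in 8.5, which was derived for downstaging (25% vs 40%, alpha 0.05, power 0.8, 10% dropout). A one-sided unpooled formula gives 117.5, so 118 per arm and 236 in total, but before dropout. No variant tried gives 236 with the 10% included. That is a separate matter; here 236 is taken as the number treated.

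**2. How attribution alone can move the endpoint.** All rates here are assumptions. Suppose 40% of patients in each arm have an all-cause grade 3 or higher event, so that the true difference is zero. The attributed rate is 0.40 × the share judged drug-related.

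| Share attributed, tablet arm | Share attributed, control | Attributed rates | Spurious difference |
|---|---|---|---|
| 90% | 80% | 36% vs 32% | +4 points |
| 90% | 70% | 36% vs 28% | +8 points |
| 80% | 90% | 32% vs 36% | −4 points |
| 90% | 90% | 36% vs 36% | 0 |

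The third row is a spurious advantage for the tablet. The documents give no basis for choosing among the rows.

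**3. Precision of an all-cause difference.** Assume 1:1 allocation (the ratio is not stated), 118 per arm and a common rate p. The half-width is 1.96 × √(2p(1−p)/n).

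- p = 0.20: 1.96 × √(0.32/118) = 0.102
- p = 0.30: 1.96 × √(0.42/118) = 0.117
- p = 0.40: 1.96 × √(0.48/118) = 0.125
- p = 0.50: 1.96 × √(0.50/118) = 0.128

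This is about ±10 to ±13 points. With 106 per arm (118 × 0.9) the range is 0.108 to 0.135. That case is pessimistic, because the Safety Set keeps anyone who received one dose and later dropouts stay in.

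**4. What such an interval could not do.** Take a true 10-point increase, two-sided 5% and 118 per arm. Power is Φ[(d√n − 1.96√(2p̄(1−p̄))) / √(p₁(1−p₁) + p₂(1−p₂))], where p̄ is the mean of the two rates. For 20% vs 30% this is Φ[(1.086 − 1.200)/0.608] = Φ(−0.187), or 43%. It is 36% for 30% vs 40%, and 34% for 40% vs 50% and for 50% vs 60%. The increase detectable with 80% power is about 16 to 18 points over control rates of 20% to 50%.

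**The case against.** The strongest reply is that the plan is silent here and not wrong. The Safety Set includes control patients, the endpoint definition is not tied to one arm, all-cause events are summarised, and the list in 8.4 is open with detail deferred. A reader might infer that the trial will leave its randomised control unused for safety. The documents do not support that: tables by arm are neither promised nor excluded. The single-regimen wording of the safety objective is also weak evidence, because every objective in 2.2 is worded that way, including the primary one, whose stated purpose is comparative.

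A reader might also infer a bias in a known direction. That is not supported either. An extra suspect drug could raise attribution in the tablet arm, while the background section's description of the tablet as having established safety could lower it. The endpoint concerns drug therapy as a whole, so a typical chemotherapy event can count in both arms, and 7.5.2 sets written criteria that constrain the judgement.

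Finally, descriptive safety analysis is usual in phase II, and a difference with an interval but no test could itself be called descriptive. That is fair, and it means the fix is compatible with 8.4.

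What remains is that nothing in 2.2, 2.3 or 8.4 commits the trial to any between-arm safety estimate, and the one named safety endpoint depends on the unblinded judgement. Low power argues for showing the interval, since bare percentages hide it.

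**Conclusion.** The point holds as a gap in specification combined with a weaker choice of endpoint. It is not an arithmetic error, and it does not show that the safety data will be unusable. The attribution shifts of 4 to 8 points illustrate the mechanism under assumed shares and do not estimate its size. The precision of about ±10 to ±13 points rests on 236 treated patients, 1:1 allocation and a common rate of 20% to 50%, none of which the documents state for safety. If the observed difference were zero, the upper limit would still lie 10 to 13 points above it, so a moderate increase could not be excluded. The change is worth making because it fixes the contrast before results are known and uses data the plan already summarises.

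**What to change.** In 2.2, 2.3(5) and 8.4, add as the main safety measure the proportion of Safety Set patients in each arm with at least one grade 3 or higher adverse event of any cause, from first dose up to surgery. Report the between-arm difference with a 95% confidence interval (for example Newcombe) and no hypothesis test. State the end of the window for patients who never reach surgery.

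The preoperative window matters. The objective concerns neoadjuvant treatment, whereas adverse events are collected until 30 days after the last study drug (7.6.1). A whole-study contrast would add surgical events and postoperative cycles in which the arms may no longer differ by the tablet.

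Keep the drug-related rate by arm, and the whole-study tables, as supportive, and say which categories of 7.5.2 count as related.

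Cost: wording in three sections and one line in a planned table, with no new data or patients. The downside is that all-cause rates are higher and include events the drugs did not cause.
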